14.2. Analysis of Outcome Measures

A separate Statistical Analysis Plan (SAP) will be produced by the Sponsor outlining the analysis of VITDALIZE, the UK specific outcomes will be appended to the SAP completed by the UK Statistician in collaboration with the UK CI. The SAP will provide a more comprehensive description of the planned statistical analyses. A brief outline of these analyses is given below. The primary comparison groups will be composed of those treated with vitamin D3 versus those treated with placebo.

Intention-to-treat (ITT) population: The primary analysis will be performed on the ITT population. The ITT population will include all patients who receive at least the loading dose of the trial medication. All patients included here will be analysed according to the treatment assignment during randomisation.

Per protocol population: The per protocol population will include all patients who received the loading dose and have a compliance >80%. Compliance is defined as self-reported percentage of doses ingested until day 90. Other protocol violations may also lead to exclusion of patients from the per protocol population. This will be discussed on an individual basis within the international trial's teams working on VITDALIZE.

Safety population: The safety analyses will be based on the treated set, which is defined as all randomised patients who receive at least 1 dose of trial medication. All patients will be analysed according to the treatment they received.

All available data will be used in the analyses and data summaries. There will be no imputation of any missing data. All outcomes will be adjusted for the baseline values (where available) and the stratification parameters (gender and centre). If covariate adjustment is not practical, then unadjusted estimates will be produced and it will be made clear in the output why this occurred, e.g. due to lack of model convergence.

14.3. **Data analysis**

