7. TRIAL TREATMENT / INTERVENTION

7.1. Treatment(s) and Dosing Schedule

The intervention is a therapeutic dose of Cholecalciferol (Oleovit D3 or vitamin D3) versus placebo in an otherwise identical oily solution of MCT, either given by nasogastric or jejunal feeding tube or swallowed. We will use the preparation that is commercially available in Europe (Cholecalciferol, 12.5ml per bottle, 400IU per drop, total dose of 180,000IU per bottle):

- Vitamin D: oral/enteral pharmacological dose of cholecalciferol (vitamin D3)
 - Loading dose of 540,000IU (dissolved in 37.5ml of MCT) followed by 4000IU daily (10 drops) for the entire active trial period (90 days) – total dose 900.000IU
- Placebo: identical regime
 - Loading dose of 37.5ml MCT followed by 10 drops daily

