8. OUTCOME MEASURES AND TRIAL PROCEDURES

Screening - Day -3 to 0

- Vitamin D analysis
- Eligibility
- Informed consent

Please note, details of the screening assessment have been described earlier in Section 6.2.

Baseline - Day 0

The patient receives the loading dose of the allocated intervention (vitamin D or placebo) and the following is recorded.

- Age
- Sex
- ICU admission diagnosis
- ICU type (medical, surgical, neurological, cardiac)
- Charlson comorbidity index (based on co-morbidities on ICU admission)
- Simplified Acute Physiology Score (SAPS III)
- Therapeutic Intervention Scoring System (TISS 28)
- SOFA score (on admission to ICU)
- Number of organ failures
- Katz Activities of Daily Life (prior to ICU admission)
- Serum calcium
- If applicable¹, patient health-related quality of life questionnaire (EQ-5D-5L and WHODAS 2.0, proxy if patient does not have capacity)
- If applicable², blood sample for future research (pre-intervention)

Please note, if there has been a >24-hour delay since eligibility was confirmed, eligibility must be re-assessed prior to the patient receiving the loading dose.

Please note, the day of the study medication loading dose is the start for the calculation of the time dependent outcome data.

The SOFA and SAPS III scores will also capture data on the presence of sepsis and renal dysfunction (our 2 predefined sub-groups).

Day 1

The patient begins daily dose treatment with allocated intervention for 90 days.

Day 5

- Survival status
- Serum calcium
- Treatment with allocated trial medication
- Trial medication compliance
- SOFA score and type(s) of organ support
- Presence of sepsis/infection
- Targeted adverse events (refer to Section 9.3.2)
- If applicable², blood sample for future research

Day 12

• If applicable², blood sample for future research

Day 28

- Survival status (primary endpoint 28-day mortality)
- Serum calcium (if still in hospital)
- Targeted adverse events (refer to Section 9.3.2)
- Treatment with allocated trial medication
- Trial medication compliance
- If applicable¹, patient health-related quality of life questionnaire (EQ-5D-5L and WHODAS 2.0, proxy if patient does not have capacity)
- If applicable¹, health economics questionnaire

Day 90

- Survival status
- · Katz Activities of Daily Living
- Targeted adverse events (including self-reported infections requiring antibiotics, self-reported falls and fracture, hospital, and ICU admissions)
- Discharge destination

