- Trial medication compliance
- If applicable¹, patient health related quality of life (EQ-5D-5L and WHODAS 2.0, proxy if patient does not have capacity)
- If applicable¹, health economics questionnaire

Day 90 marks the end of the trial intervention.

1 year

- Survival status
- If applicable¹, patient health related quality of life (EQ-5D-5L and WHODAS 2.0, proxy if patient does not have capacity)
- If applicable¹, health economics questionnaire

Information obtained at day 28, 90 and 1 year (see above) can be obtained from the hospital's data management systems or via telephone interview with the trial patient or delegated family member. Additional information will be obtained from reviewing hospital clinical records and via NHS Digital and if applicable¹, patient Health economics questionnaire.

The following questionnaires will not be collected for patients recruited post substantial amendment 5 (SA5) implementation:

- EQ-5D-5L
- WHODAS 2.0
- Health economics questionnaire

¹ Only applicable if patient recruited pre-SA5 implementation

² Only applicable if patient recruited pre-SA5 implementation and consents to the sub-study

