8.1. Primary Outcome

• All-cause mortality at 28 days after randomisation

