14.3.3. Primary Outcome Measure

The primary outcome, 28-day mortality will be displayed using Kaplan Meier estimates of survival curves in each treatment. A mixed effects Cox Proportional Hazard model including

centre as a random effect will be fitted to obtain an adjusted hazard ratio and 95% confidence interval. For the UK arm only, a complier average causal effect (CACE) analysis will also be performed for the primary outcome. Details of the primary outcome analysis will be defined in the SAP approved by the Sponsor and approved by the international DMC prior to any interim analysis. The UK specific outcomes will be defined in a separate SAP that will describe all of the statistical analysis that will be undertaken for the UK arm only and appended to the Sponsor approved SAP.

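### The per-protocol compliance rule runs to day 90 and is silent on deaths, so a per-protocol comparison of 28-day mortality would be selected on the outcome

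*Protocol*

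**What the plan says.** Protocol section 14.2 sets the population: "The per protocol population will include all patients who received the loading dose and have a compliance >80" per cent. It then gives the only definition of compliance in the document: "Compliance is defined as self-reported percentage of doses ingested until day 90". It states neither the denominator nor how a patient who dies before day 90 is scored, and it rules out imputation of missing data.

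The surrounding text is as follows:

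- **Endpoint (section 8.1):** "All-cause mortality at 28 days after randomisation".
- **Dosing (section 7.1):** a loading dose, "followed by 4000IU daily (10 drops) for the entire active trial period (90 days"), for a stated total of 900,000 IU. Section 8 starts the daily doses on day 1: "The patient begins daily dose treatment with allocated intervention for 90 days".
- **Records (section 8):** "Trial medication compliance" is listed at days 5, 28 and 90. Information at day 28, day 90 and 1 year may come from hospital data systems or "via telephone interview with the trial patient or delegated family member".
- **Primary analysis (section 14.2):** assigned to the ITT population, not the per-protocol set.
- **CACE (section 14.3.3):** "For the UK arm only, a complier average causal effect (CACE) analysis will also be performed for the primary outcome". A complier is not defined, and details of the primary outcome analysis are left to the SAP.

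**The concern.** A per-protocol set for a 28-day endpoint should be fixed by what happened up to day 28. This rule uses the whole 90-day course. A patient who dies early has no chance to accumulate most of those doses, and a survivor can fail the threshold through events that come after the endpoint has been settled. Either way, vital status at day 28 helps to decide who is analysed.

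A per-protocol result on mortality is usually read as supporting or weakening the primary result. One built on this rule could do neither. Because the denominator is open, it would also have to be chosen later, possibly with data in view.

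**Working it through.** **1. Reproducing the plan's figures (section 14.1).** With 25% vs 20% mortality, HR = ln(0.80)/ln(0.75) = 0.776 (stated 0.78). At 80% power and two-sided 5% alpha, Freedman's formula gives 492 events, and 492/0.225/2 = 1093 per group (stated 1093). Schoenfeld's formula gives 487 events (stated 486). The assumptions can therefore be used as they stand. With N = 2400 allocated 1:1, expected 28-day deaths are 1200 × 0.25 + 1200 × 0.20 = 300 + 240 = 540.

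**2. Gap between endpoint and compliance window.** 90 − 28 = 62 days.

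**3. Reading A: the denominator is the full 90-day course.** Take a patient who dies on day 28 having taken every dose due:

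| How doses are counted | Maximum compliance | Daily doses needed to exceed 80% |
|---|---|---|
| Daily doses only | 28/90 = 31.1% | 73 (72/90 is exactly 80%) |
| Loading dose counted as one dose | 29/91 = 31.9% | 72 (73/91 = 80.2%) |
| International units | (540,000 + 28 × 4,000)/900,000 = 652,000/900,000 = 72.4% | 46 (724,000/900,000 = 80.4%) |

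The cut-off day depends on the count, but a 28-day death fails under all three. The set would contain 0 of about 540 expected deaths: 0% mortality in both arms and no estimable hazard ratio.

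**4. Reading B: the denominator is doses due while alive.** A fully adherent patient who dies on day 20 scores 20/20 = 100% and stays in. A patient equally adherent to day 28 who survives but takes nothing after day 40 scores 40/90 = 44.4% and is removed. Section 7.6.3 makes this possible, since misplaced medication is not replaced. Both had complete exposure over the period that matters for the endpoint.

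To see the effect, suppose everyone is fully adherent to day 28, and let s be the share of 28-day survivors removed for missed doses afterwards. Mortality in the set becomes p/[p + (1 − p)(1 − s)], which exceeds the true p in any arm with s > 0. The odds ratio (vitamin D vs placebo) is multiplied by (1 − s in placebo)/(1 − s in vitamin D). It is preserved only if late non-adherence is equal in the two arms; the absolute risks are wrong even then. The documents give no value for s, so no size is claimed for this reading.

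**5. CACE, conditional on the same rule being adopted with reading A.** CACE = ITT difference / proportion of compliers. With 20% dead by day 28 in the vitamin D arm and perfect adherence while alive, compliers are at most 80%. A true 5.0-point difference would be reported as at least 5.0/0.80 = 6.25 points, which is 25% too large. Deaths from day 29 until the threshold is reached would raise it further. Death would make treated patients non-compliers, contrary to the exclusion restriction.

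**The case against.** The strongest reply is that the text does not go as far as its worst reading. A reader might infer that every patient who dies by day 28 is certainly excluded. That holds only with a 90-dose denominator, which section 14.2 does not state; under doses due while alive, adherent early deaths are not removed by arithmetic. This stands, and the loss of all events is claimed for reading A only. It does not rescue the rule, because reading B still removes survivors for conduct after day 28.

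A reader might also infer that the dead and the sedated can have no compliance value because it must be self-reported. Section 8 does not support that: compliance is recorded at days 5 and 28, and hospital systems or a family member may supply information. The self-report wording in section 14.2 fits poorly with those sources, but the mismatch does not show that deaths are unclassifiable.

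A third tempting inference is that the UK CACE is invalid. The protocol does not tie it to the per-protocol rule, and a CACE analysis would normally keep all randomised patients. The 6.25-point figure is therefore a warning about one possible choice.

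Finally, no section names the outcomes for which the per-protocol set will be used, and use for day-90 outcomes would suit the definition. That is fair. But the set is defined without restriction in a trial whose primary outcome is 28-day mortality, so this use is the obvious one to guard against.

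**Conclusion.** The point holds in conditional form. The only written compliance rule extends 62 days past the primary endpoint and leaves deaths unaddressed. If the per-protocol set is applied to 28-day mortality, the 90-dose reading leaves 0 of about 540 expected deaths (assuming 25% and 20% mortality and 1200 per arm). The while-alive reading filters survivors but not deaths on later adherence, with a bias whose size the documents do not allow to be calculated.

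The ITT primary analysis, the sample size and the interim boundary do not depend on this rule. The CACE analysis is exposed only if it borrows the rule. This should be fixed, but it does not threaten the trial's main result.

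**What to change.** For 28-day mortality, define per-protocol adherence as doses taken divided by doses due from day 0 to the earliest of day 28, death or withdrawal. Use the compliance data already collected at days 5 and 28: hospital records while the patient is in hospital, and self-report or family report after discharge. State how a missing report is classified. Keep the day-90 definition for day-90 outcomes only, and list which outcomes each version serves.

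For the UK CACE, define a complier by an exposure that survival cannot determine, such as receipt of the loading dose among all randomised patients. Say explicitly that the per-protocol threshold is not used there.

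The cost is wording in section 14.2, section 14.3.3 and the SAP. The day 5 and day 28 compliance items are already in the assessment plan, so no new visit is needed. The change should be made before anyone sees outcome data by arm.

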14. STATISTICAL CONSIDERATIONS

14.1. Sample Size

The sample size for the multinational trial is based on the primary endpoint 28-day mortality. In the VITdAL-ICU trial, in the pre-defined subgroup with severe VDD, 28-day mortality rates of 36% (37/102) in the placebo group and 20% (20/98) in the vitamin D group were observed (51). The VITDALIZE trial has been designed to be powered to detect a smaller, but clinically relevant absolute mortality difference of 5% with a power of 80% or a 6% difference with 90% power with an assumed baseline mortality rate of 25% (close to the lower limit of the 95% CI of the 36% mortality observed in VITdAL-ICU). This corresponds to a clinically important relative risk reduction of between 20% and 24%. Using a fixed sample size design and a 2-sided log-rank test for equality of survival curves with a 2-sided alpha level of 5%, a sample size of over 1000 patients per group will be needed (total sample size of approximately 2200). The table below shows this, and varies the baseline event rate from 25% to 30% to illustrate that our assumptions are robust to modest variations in our assumptions.

Placebo 28-day all-cause mortality	25%		30%	
	80% power	90% power	80% power	90% power
VitD 28-day all-cause mortality	20%	19%	25%	24%
Hazard ratio	0.78	0.73	0.81	0.77
N = (per group)	1093	1002	1248	1149
Total number of events required	486	434	686	620
N = (total)	2186	2004	2496	2298

Accounting for a drop-out rate of approximately 10% yields a total sample size of N=2400 patients with the UK contributing 25% of the sample size with 600 patients. Loss to follow up in critical care trials for 28-day mortality is low and is approximately 3% in previously published critical care trials (51, 56, 57) so this 10% estimate of loss to follow up is also conservative.

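### A cheap gain in power is left unused: as ordinarily read, the primary 28-day mortality model adjusts only for sex and centre, although age and SAPS III are scheduled at Day 0

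*Protocol*

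**What the plan says.** Section 14.2 gives the adjustment rule: "All outcomes will be adjusted for the baseline values (where available) and the stratification parameters (gender and centre"). Section 14.3.3 specifies the primary analysis as "A mixed effects Cox Proportional Hazard model including" centre as a random effect, giving an adjusted hazard ratio with a 95% confidence interval. It names no other covariate and leaves details to a sponsor SAP.

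The Day 0 list in section 8 includes age and "Simplified Acute Physiology Score (SAPS III"). The schedule in section 8.5 also places SAPS III at baseline.

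The design test is different. Section 14.1 sizes the trial on a "2-sided log-rank test for equality of survival curves with a 2-sided alpha level of 5" per cent, and section 14.7 bases the interim stopping rule on a log-rank p-value below 0.003. Sections 14.2 and 14.3.6 both rule out imputation of missing data.

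**The concern.** Sex and centre balance the randomisation, but neither measures how ill a patient is. A severity score and age would normally be expected to tell much more about who dies within 28 days. In a Cox model, leaving out a strong predictor weakens the treatment test; including it recovers power without another patient.

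Randomisation is stratified by site and sex only (section 3.1), so any chance imbalance in severity is left to the analysis. Without a prespecified severity adjustment, a response to such an imbalance would be post hoc and open to dispute.

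A wider reading of the phrase about baseline values, as any baseline variable, does not help. The primary covariate set would then be undefined, and the remedy would be the same: name the covariates.

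**Working it through.** **Inputs (section 14.1).** The target is an "absolute mortality difference of 5% with a power of 80% or a 6% difference with 90% power", "with an assumed baseline mortality rate of 25" per cent. The table gives 20% under "VitD 28-day all-cause mortality" and 486 under "Total number of events required" for 80% power, with 1093 per group (2186 in total). The total of 2400 allows about 10% drop-out, which leaves 2400 × 0.90 = 2160 evaluable.

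**Step 1: reproduce the plan's figure.**
- HR = ln(0.80)/ln(0.75) = 0.2231/0.2877 = 0.776, so |ln HR| = 0.254.
- Schoenfeld events = 4 × (1.960 + 0.842)² / 0.254² = 487. At mean mortality 22.5% this is 1083 per group.
- Freedman's formula gives 492 events and 1094 per group. The two-proportion formula gives 1094 per group.
- Power with 486 events = Φ(√(486/4) × 0.254 − 1.960) = Φ(0.840) = 80.0%.

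The plan's 486 events, 1093 per group and 80% are reproduced. At 2160 evaluable patients the expected events are 2160 × 0.225 = 486, so power there is about 80%.

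**Step 2: power with adjustment.** Cox trials were simulated with 2160 patients, 1:1 allocation, censoring at day 28 and marginal mortality held at 25% and 20%. One standard normal index stood for age and SAPS III combined. The strength of that index is an **assumption**, expressed as the AUC for 28-day death. There were 1500 replicates per row, with Monte Carlo error of about 1 point; a separate run of 2500 replicates agreed. The factor is the equivalent multiplication of sample size, rounded.

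| Assumed AUC | Simulated power, without index | Simulated power, with index | Factor f |
|---|---|---|---|
| 0.63 | 80.4% | 81.1% | 1.04 |
| 0.68 | 81.1% | 83.7% | 1.10 |
| 0.73 | 78.9% | 86.0% | 1.19 |
| 0.78 | 79.4% | 90.3% | 1.33 |

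The second column varies only by simulation noise around 80%. The gain is 1-2 points for a weak index and about 3-10 points for a moderate to good one. With all 2400 evaluable, power goes from about 83-84% to about 85-86%, 87%, 89-91% and 92%.

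**Step 3: what missing scores would do.** With no imputation, a patient lacking a covariate leaves the model. If a fraction m is dropped, power = Φ(√(486 × f × (1 − m)/4) × 0.254 − 1.960). The gain is cancelled when f(1 − m) = 1, that is at m = 1 − 1/f.

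| Assumed AUC | m = 0 | m = 5% | m = 10% | Gain cancelled at m |
|---|---|---|---|---|
| 0.63 | 81% | 79% | 77% | 4% |
| 0.68 | 84% | 82% | 80% | 9% |
| 0.73 | 86% | 85% | 83% | 16% |
| 0.78 | 90% | 88% | 87% | 25% |

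**Step 4: change of estimand.** At AUC 0.73 the hazard ratio conditional on the index is about 0.757, against 0.776 marginally, for the same 25% and 20% risks.

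**The case against.** The strongest reply is that nothing here is wrong. Adjusting for the stratification factors is sound, the sample size reproduces, and section 14.3.3 sends the details to a SAP that is not shown and may already list age and SAPS III. This stands in part. A reader might infer that both variables are definitely unused, and the documents do not establish that. They do state a rule for all outcomes, and a SAP that followed it as ordinarily read would omit both.

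A reader might also infer that the trial is underpowered, since 2160 falls short of 2186. The documents do not support that. The shortfall is trivial, and section 14.1 calls 10% loss conservative against about 3% in earlier trials. At 3% loss, 2400 × 0.97 = 2328 patients and 2328 × 0.225 = 524 events give about 83% power.

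Nor is the gain free or certain. It depends on an AUC that the documents do not give, and it can vanish if scores are missing; the protocol schedules SAPS III but says nothing about its completeness. Adding covariates to the Cox model does nothing for a log-rank test, so the benefit requires the adjusted model to be the confirmatory test. All of this stands, and the fix has to deal with it.

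**Conclusion.** This is a cheap improvement and not an error. As ordinarily read, the protocol adjusts the primary mortality model for sex and centre only and leaves two scheduled baseline variables unused. At 2160 evaluable patients, using them is worth about 1-2 points of power if they predict weakly (AUC 0.63) and about 3-10 points if they predict moderately to well (AUC 0.68 to 0.78).

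Those figures assume proportional hazards, a correctly specified index, no centre or sex effects in the simulation, near-complete covariates, and the adjusted Cox test as the confirmatory test. The plan's own 80% remains correct for the unadjusted design.

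**What to change.** Before unblinding:

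- Specify the final primary model as Cox with treatment, sex, age and continuous SAPS III as fixed effects and centre as a random effect.
- State that its treatment test is the confirmatory test, since sections 14.1 and 14.7 use the log-rank test.
- Use the same test at the interim only if that analysis has not yet been done, which the protocol does not say. Otherwise leave the log-rank interim rule as it is.
- Allow simple imputation of missing baseline covariates only, as an explicit exception to the no-imputation rule in sections 14.2 and 14.3.6.
- Report alongside it the model with sex and centre only, and the standardised 28-day risk difference, because the trial is powered on an absolute difference.

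The cost is wording in the protocol as well as the SAP, with no new data or patients. The downsides are a hazard ratio that becomes conditional on severity and an exception to the no-imputation text.

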6.3. Randomisation

Randomisation will be provided by a secure online randomisation system 'Randomizer' developed by the Institute for Medical Informatics, Statistics and Documentation, Medical University of Graz, Austria (available at https://www.randomizer.at/random/login). Patients will be randomised at the level of the individual in a 1:1 ratio to either high dose vitamin D3 or placebo and stratified by trial site and sex ensuring allocation concealment. An independent statistician at the Medical University of Graz will set up the trial and have access to the trial allocations in the 'Randomizer'.

Data obtained during randomisation for the VITDALIZE Trial will be stored electronically by the Sponsor. The randomisation set-up, including all patient randomisations, will be downloaded prior to database lock for storage in the VITDALIZE Trial data file at the Medical University of Graz. Randomisations performed at UK specific sites will be requested by BCTU for storage in the UK Trial Master File (TMF) prior to database lock.

Following randomisation, a confirmatory e-mail will be sent to the randomising user, , VITDALIZE UK Trials Team, UK and international CI, all of whom will have been assigned permissions on the randomisation database. The randomising user should forward the confirmatory e-mail to any other appropriate site staff, including pharmacy staff. Unique log-in usernames and passwords will be provided to those who wish to use the online system and who have been delegated the role of randomising patients into the trial as detailed on the VITDALIZE UK Trial Signature and Delegation Log. The online randomisation system will be available 24 hours a day, 7 days a week, apart from short periods of scheduled maintenance. There will be no paper randomisation available for the VITDALIZE UK Trial.

After eligibility has been confirmed and informed consent has been received, the patient will be randomised into the trial. For a patient to be randomised into VITDALIZE UK, the research team at site will complete the following:

- The Eligibility Checklist Form: Sites should complete this form prior to randomisation to
 confirm that all the necessary information (inclusion/exclusion) prior to randomisation is
 captured. If there has been a >24-hour delay since eligibility was confirmed,
 eligibility must be re-assessed and eligibility checklist completed prior to
 randomisation.
- The research team at site will 'create a new patient' using Clincase

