14.3.4. Secondary Outcome Measures

ICU, hospital mortality, 90-day mortality and 1-year mortality will be analysed using the same methods as described for the primary outcome. For any other secondary outcomes that are continuous, these will be analysed using mixed effects linear regression model. The safety outcomes, (hypercalcemia on day 5, new kidney stones, self-reported falls, and fractures until day 90) will be analysed as binary variables and compared using a mixed effects binomial model.

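### The only written fallback when covariate adjustment fails is no adjustment at all, although simpler models would keep the randomisation strata and any baseline value

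*Protocol*

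**What the plan says.** Randomisation is 1:1 and "stratified by trial site and sex ensuring allocation concealment" (Protocol 6.3).

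Section 14.2 sets the adjustment: "All outcomes will be adjusted for the baseline values (where available) and the stratification parameters (gender and centre"). The next sentence gives the fallback: "If covariate adjustment is not practical, then unadjusted estimates will be produced and it will be made clear in the output why this occurred", followed by the example "e.g. due to lack of model convergence".

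The named outcome models are mixed models:
- **Mortality (14.3.3):** a mixed effects Cox model with "centre as a random effect will be fitted to obtain an adjusted hazard ratio and 95% confidence interval". Section 14.3.4 applies the same methods to the other mortality outcomes.
- **Continuous secondary outcomes (14.3.4):** "these will be analysed using mixed effects linear regression model".
- **Safety outcomes (14.3.4):** these "will be analysed as binary variables and compared using a mixed effects binomial model".

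Sections 14.3.1 to 14.3.6 add no step between the adjusted model and the unadjusted estimate. Section 14.2 also says "The SAP will provide a more comprehensive description of the planned statistical analyses". That SAP is not at hand.

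**The concern.** The rule goes from full adjustment to none in one step. In a mixed model the part most likely to fail is the centre random effect, for example with many small units, or with rare events in a binomial model. This is general statistical experience, not something the protocol states. Failure of one variance component is no reason to remove sex and the baseline score, which are ordinary fixed covariates. Nor does it require removing centre altogether, because a stratified or coarsened centre term needs no variance component.

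The trigger is also loose. The protocol does not define when adjustment counts as impractical, and non-convergence is only one example. The choice between an adjusted and an unadjusted headline result can therefore be made after the data are seen. Giving the reason in the output discloses that choice but does not pre-specify it.

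At stake is precision. An unadjusted analysis of a stratified trial has standard errors that are somewhat too large when the strata are prognostic. Where a baseline score exists, its contribution is lost too.

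**Working it through.** **1. The plan's own figure.** Section 14.1 gives 1093 per group and 486 events for 25% v 20%, 80% power, two-sided 5% log-rank.
- Hazard ratio = ln(0.80)/ln(0.75) = 0.776.
- Schoenfeld: 4 × (1.960 + 0.842)² / (ln 0.7757)² = 487 events, and 487/0.225/2 gives 1083 per group.
- Freedman: 492 events, 1094 per group.

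The figure reproduces. It rests on a plain log-rank test with no stratification or adjustment.

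**2. What the fallback removes, by outcome**

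| Outcome | Baseline value of the outcome? | Lost under the fallback |
|---|---|---|
| Mortality | No | Sex, centre |
| Binary safety events | No | Sex, centre |
| SOFA (day 0 and day 5) | Yes | Sex, centre, baseline |
| Katz (before ICU, day 90) | Yes | Sex, centre, baseline |

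EQ-5D-5L and WHODAS 2.0 belong with the last two rows for patients in whom they are collected.

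**3. Losing the strata: mortality.** The protocol gives neither the number of centres nor the between-centre variation, so both are assumed. The first simulation used 60 centres × 36 patients = 2160, blocks within site and sex, 25% v 20%, and 1500 trials per scenario. Monte Carlo error is about 1 point for power and 0.5 point for type I error.

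| SD of centre log hazard | Power, unadjusted v centre-stratified log-rank | Difference (points) | Type I error, unadjusted v stratified |
|---|---|---|---|
| 0.3 | 79.7% v 79.8% | 0.1 | 4.2% v 4.2% |
| 0.5 | 81.9% v 83.3% | 1.4 | 4.3% v 4.9% |
| 0.7 | 79.5% v 83.6% | 4.1 | 3.6% v 4.7% |

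A second simulation used a binary outcome, 2400 patients, 60 centres and 3000 trials, comparing the crude test with a Mantel-Haenszel test stratified by centre and sex. For centre SDs of 0.3, 0.6 and 0.9 on the logit scale:
- Power was 84.2% v 84.5%, 85.5% v 86.7% and 85.8% v 88.5%.
- Type I error was 4.4% v 4.7%, 4.3% v 5.1% and 3.3% v 4.9%.

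A normal approximation agrees. Let the strata carry a share s of the variance. The true type I error of the unadjusted test is 2Φ(−1.960/√(1−s)), and its power is Φ(2.802 − 1.960/√(1−s)) when the adjusted test has 80%. For s = 2%, 5% and 10%, type I error is 0.048, 0.044 and 0.039, and power is 79.4%, 78.5% and 76.9%.

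**4. Losing the baseline: continuous outcomes.** The protocol gives no correlation r between baseline and follow-up, so r = 0.5 to 0.7 is assumed, with equal variances at the two times. The reference is the baseline-adjusted analysis, with variance proportional to 1 − r².
- Follow-up score alone (for example Katz at day 90): ratio 1/(1 − r²) = 1.33 at r = 0.5 and 1.96 at r = 0.7.
- Change score (section 8.2 words the SOFA outcome as a change): ratio 2(1 − r)/(1 − r²) = 2/(1 + r) = 1.33 at r = 0.5 and 1.18 at r = 0.7.

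If the adjusted analysis has 80% power, unadjusted power is Φ(2.802/√ratio − 1.960):
- Follow-up score alone: 68% at r = 0.5 and 52% at r = 0.7.
- Change score: 68% at r = 0.5, and Φ(2.802 × √0.85 − 1.960) = Φ(0.62) = 73% at r = 0.7.

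**The case against.** The strongest reply has four parts.

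- **The fallback is valid and disclosed.** Under randomisation the unadjusted comparison is not biased towards a false positive. Any error is on the conservative side, and the reason must be reported. This stands. A reader might infer that the fallback threatens the trial's type I error, but the figures above show the opposite direction, and at low centre variation no difference at all.
- **The primary outcome was designed without adjustment.** Section 14.1 sizes the trial on a plain log-rank test, and section 14.7 uses the log-rank p-value for early stopping. Unadjusted power in the first simulation is 79.5% to 81.9%, which is essentially the planned 80%. This also stands. What is forgone is a gain over the plan, not a shortfall against it.
- **The joint loss falls where failure is least likely.** Rare safety events, where a mixed binomial model may well fail, have no baseline value. Continuous scores use a linear mixed model, which usually still returns adjusted estimates when the centre variance is near zero. This stands as a limit on how often the larger loss would occur.
- **Fallback ladders belong in the SAP, and any convergence trigger depends on the data.** This stands only in part. The protocol does not leave the step open: it writes a rule, and a better SAP ladder would have to be reconciled with it. A defined convergence failure is still much narrower than an undefined judgement that adjustment is impractical.

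**Conclusion.** The point holds as a small improvement. The protocol writes a single fallback that drops more than it needs to, on a trigger it does not define. For mortality and the binary safety outcomes only sex and centre go. The primary outcome loses about 0 to 4 power points, under an assumed 60 centres and assumed centre SDs of 0.3 to 0.7 on the log hazard. For continuous outcomes strata and baseline go together. With r assumed at 0.5 to 0.7, variance rises by 33% to 96% for a follow-up score analysed alone, and by 33% to 18% for a change score.

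Two stronger readings are not supported. One is that SOFA could suffer the 96% inflation: section 8.2 words that outcome as a change, so the smaller figures apply if the unadjusted analysis uses the change score. The other is that the SAP lacks an intermediate step: it has not been seen.

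**What to change.** Replace the fallback sentence in section 14.2 with an ordered rule, triggered only by a defined convergence failure. The rule should simplify the centre term first and keep sex and baseline:

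- **Mortality:** Cox model stratified by centre, with sex as covariate.
- **Continuous outcomes:** linear model with the centre effect coarsened (for example to country) or dropped, keeping sex and the baseline value.
- **Rare binary outcomes:** Mantel-Haenszel, or Poisson regression with robust standard errors, keeping sex and, where feasible, centre or country.
- **Unadjusted estimates:** a supplement or last resort only.

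Keep the existing commitment to state in the output which step was used and why, and align the SAP with the new wording. This takes two or three lines in the protocol and SAP, and slightly more analysis work. It needs no new data or patients and does not change the sample size. It should be settled before unblinded data are analysed.
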